## 17. Data analysis plan

### 17.1 Sample size determination

This is a two-arm randomized controlled trial that will assess feasibility of delivering a Mediterranean Diet intervention to patients undergoing chemotherapy, as well as the preliminary efficacy of a Mediterranean Diet intervention vs. usual care on the prevention of cancer-related fatigue. Our sample size is based on our fatigue outcome as measured using the FACIT-F fatigue subscale, which is a 13-item scale with responses that range from 0-4; the FACIT-F subscale score ranges from 0-52 and a higher score indicates greater wellbeing and less fatigue. The minimal clinically important difference for the FACIT-F is 3 points.

We plan to recruit a total of 42 participants and randomize them in a 2:1 ratio, intervention: control (28:14) using computer-generated block randomization with blocks of 3 or 6. Patients will be stratified based on how frequently their chemotherapy is planned to be administered. One strata will include patients who plan to receive weekly, biweekly (Q2w), or every 4-week (Q4w) regimens, and the other strata will include those on other regimens (e.g., Q3w). Thus, those in the first strata will complete 4-week and 8-week assessments for our study at the end of a chemotherapy cycle, while those in the second strata will be completing assessments in the middle of their cycle. (If there are

**Fig. 3.** Effect size vs. sample size at 70% and 80% power with 33 participants on the study.

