dose delays or changes to the chemotherapy schedule, we will still collect assessments at the originally planned time.) We estimate attrition between approximately 20 and 25%, thus we estimate to retain 33 (22:11) evaluable patients. This sample size is appropriate for small randomized pilot studies and it will allow us to obtain preliminary estimates of descriptive statistics [mean, standard deviation (SD), and confidence intervals (CI)]. The primary endpoint is the change in fatigue as measured by FACIT-F from baseline (T1) to 4 weeks (T2). Assuming a correlation of 0.50 between T1 and T2 FACIT-F measurements, a total sample size of n=33 will provide 80% power at the 0.15 two-sided significance level to detect an effect size (ES, standardized mean between-group difference) of 0.75 of the intervention effect on change in T2-T1 FACIT-F using analysis of covariance (ANCOVA) with T1 FACIT-F as a covariate (**Fig. 3**). The estimates of T1-T2 correlation and attrition rate are based on our prior studies.

Feasibility is often determined for nutrition interventions among 10-15 participants (e.g.,); pilot preliminary efficacy studies usually recruit 20-30 (e.g.,). **Table 6** below shows prior studies that are similar to this one, including their sample size.

Study	n	Population	Intervention	Outcome	Results
Zick et al. (2017) 	30	breast cancer survivors	Fatigue reduction diet vs. General Health Curriculum (time and attention control) for 3 months	Brief Fatigue Inventory	From baseline to 3-months, fatigue improved by 44±39% in diet group compared to 8±34% in the control group (p=0.01)
Skouroliakou et al. (2018) 	70	breast cancer survivors	Mediterranean Diet for 6 months vs. handout	serum antioxidant capacity and body composition	The dietary intervention based on Mediterranean Diet improved serum antioxidant capacity, body composition, and glycemic profile.
McMillan et al. (2011) 	27	healthy women in their 20's	Mediterranean Diet vs. control for 10 days	Profile of Mood States	A group × time interaction demonstrated that the Mediterranean Diet reduced fatigue (p=0.16) and improved vigor (p<0.01).

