#### *17.4.2 Aim 2: Patient-reported fatigue*

To provide estimates of efficacy comparing the Mediterranean Diet to usual care for alleviating fatigue, we will evaluate between-arm difference in mean change in FACIT-F fatigue subscale score from baseline to 4 weeks in an ANCOVA model. The outcome will be FACIT-F fatigue score at 4 weeks with arm included as a fixed effect and FACIT-F fatigue score at baseline as a covariate. To assess the moderating effect of the baseline level of fatigue we will test arm×baseline interaction. To further evaluate the longitudinal trajectory of fatigue and the maintaining effect of the intervention, we will incorporate FACIT-F fatigue score measured at all time points (T1, T2, T3) in a repeated measures linear mixed model. The impact of patient's variables (e.g., age, gender, body mass index) on the results will be assessed by adding the covariates to the models. The results of the analyses together with the estimates of distribution parameters (e.g., mean, SD) of T1-T3 FACIT-F fatigue score values as well as the change scores will be used in planning a future randomized trial.

We expect all measures of cancer-related fatigue to increase over the course of chemotherapy, though we hypothesize that the differences will be attenuated in the intervention group. We will also compare our baseline-to-post-intervention change scores to those obtained via historical controls (e.g., [name] et al., 2018).

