#### *17.4.3 Mechanistic aims*

We will assess the preliminary efficacy of the Mediterranean Diet intervention on metabolic measures including mitochondrial function from freshly isolated T cells. We will also obtain preliminary data on effects of the Mediterranean Diet vs. usual care on established metabolic biomarkers from blood samples. In an exploratory analysis, we will use similar models as in Aim 2 to assess Mediterranean Diet score with biomarkers of metabolic function. We will use both ANCOVA models looking at data at 4 or 8 weeks adjusting for baseline values, and longitudinal models incorporating data from time points T1-T3. This battery of biomarkers will be assessed to determine which are the most useful, and which others we should include in follow-up studies. Special statistical considerations may arise and will need be addressed during the analysis of biomarkers, including the need for transformation and missing data due to the detection limits.

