#### *17.4.4 Exploratory analyses*

In an exploratory analysis, we will correlate Mediterranean Diet score with patient-reported fatigue using the FACIT-F fatigue score at 4 weeks and 8 weeks. We expect that the majority of participants will improve their Mediterranean Diet score, and that 4 and 8 week scores will range from 5-14 in the intervention group (higher is better). We expect that the fatigue subscale of the FACIT-F will range from 0-43 out of 52 based on a historical dataset (Kleckner et al.; a higher score indicates less) and that FACIT-F total scores will range from 44-160 out of 160^161 (higher is better well-being). We will also assess correlations between baseline Mediterranean Diet score (proxy for improvement in diet quality) and change in fatigue to evaluate the influence on baseline diet on the development of fatigue. Further, we will assess the change in the Mediterranean Diet score and the change in fatigue to see if a greater shift in diet led to a greater prevention of fatigue.

Other measures collected via patient-reported outcome questionnaires (e.g., BFI, Fact-Cog) will be analyzed using similar methodology as outlined in the Aim 2 (FACIT-F score analysis).

**Because of the small sample size in this study and the resulting low statistical power, these secondary and exploratory analyses will be interpreted very cautiously and only used to aid in the designing of a study for our larger trial and generation of new hypotheses.**

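### The three-visit FACIT-F mixed model does not say how baseline is handled; fitted in its usual form, it gives a less precise week-8 arm effect than the same data allow

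*Combined protocol and SAP*

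**What the plan says.** Section 17.4.2 specifies the week-4 comparison fully: an ANCOVA of the week-4 FACIT-F fatigue score on arm and baseline score. Section 17.1 does its power calculation for that model, "using analysis of covariance (ANCOVA) with T1 FACIT-F as a covariate". It states that "a total sample size of n=33 will provide 80% power at the 0.15 two-sided significance level", for a standardised difference between arms of 0.75. It assumes a correlation "of 0.50 between T1 and T2 FACIT-F measurements".

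For the trajectory and the persistence of any effect, Section 17.4.2 adds only that "we will incorporate FACIT-F fatigue score measured at all time points (T1, T2, T3) in a repeated measures linear mixed model". On this wording T1 is a response. The section does not give the fixed effects, say whether the arms share a T1 mean, name a covariance structure, or say which contrasts are the week-4 and week-8 effects.

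The approach carries over elsewhere. Section 17.4.3 plans "longitudinal models incorporating data from time points T1-T3" for biomarkers, alongside baseline-adjusted ANCOVA at 4 or 8 weeks. Section 17.4.4 says the other questionnaires "will be analyzed using similar methodology as outlined in the Aim 2".

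The documents describe no other between-arm FACIT-F analysis that includes week 8. The week-8 correlations with diet score in Section 17.4.4 and the historical-control comparison in Section 17.4.2 do not compare the randomised arms.

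**The concern.** A reader would ordinarily take a repeated measures model of this kind to contain arm, time and arm-by-time terms, with each arm free to have its own T1 mean. The week-4 and week-8 arm effects are then differences in change from T1. That form estimates a T1 difference whose true value is zero. Arms are assigned at random, and Section 8.2.5 reveals the assignment only after the baseline assessments. Chance imbalance at T1 is then subtracted in full, instead of in proportion to the correlation.

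At stake is the precision of the only week-8 fatigue comparison between arms, in a pilot whose estimates are meant to plan the next trial. The model could also give a week-4 effect that differs from the ANCOVA effect, and the plan does not say which model the week-4 and week-8 contrasts come from. Section 8.2.5 records that the unblinded principal investigator takes part in the analysis, which is a further reason to settle the form in advance.

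**Working it through.** **Inputs.** From Section 17.1: 22 and 11 evaluable participants from 28 and 14 randomised; ES 0.75 SD; two-sided alpha 0.15; T1–T2 correlation 0.50. Assumed, because the documents do not say: equal variance at each visit, the T1–T3 correlation, and the dropout pattern. Variances below are in units of σ²(1/22 + 1/11).

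**The plan's own figure.** The ANCOVA variance factor is 1 − ρ² = 1 − 0.25 = 0.75. The SE is √(0.75 × 0.1364) = 0.320 SD, so the noncentrality is 0.75/0.320 = 2.345. With 30 df the critical value is 1.477 and power is 80.6%. The stated 80% is reproduced.

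**Effect of baseline handling, 33 completers.**
- Separate T1 means by arm, contrast of change from T1: 2(1 − ρ) = 1.00 at ρ = 0.50.
- One common T1 mean, or T1 as covariate: 1 − ρ² = 0.75.
- Ratio: 2(1 − ρ)/(1 − ρ²) = 2/(1 + ρ) = 1.33, so the SE is √1.333 = 1.155 times as large.

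To show what that means, take the plan's ES and alpha. The SE of the change contrast is √0.1364 = 0.369 SD, the noncentrality is 2.031, and power is 71% against 81%. This is an illustration only, since the plan claims no power for the mixed model.

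**Week 8 with dropout.** Suppose all 42 have T1 and 33 reach T3. Write A for the variance with a common T1 mean. The free-baseline estimate equals that estimate minus (1 − ρ) times the T1 arm difference in all 42. The two parts are independent, so its variance is A + (1 − ρ)² × (1/28 + 1/14)/(1/22 + 1/11) = A + (1 − ρ)² × 0.786.

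For illustration, six are lost after T1 (4:2) and three after T2 (2:1), with an assumed T2–T3 correlation of 0.6. A comes from the generalised least squares information matrix.

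| T1–T3 correlation | Completers: free / common | Ratio | Dropout: free / common | Ratio |
|---|---|---|---|---|
| 0.5 | 1.00 / 0.75 | 1.33 | 0.9328 / 0.7364 | 1.27 |
| 0.4 | 1.20 / 0.84 | 1.43 | 1.1051 / 0.8222 | 1.34 |
| 0.3 | 1.40 / 0.91 | 1.54 | 1.2725 / 0.8875 | 1.43 |

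The dropout pattern matters little. At 0.5, losing all nine after T1 gives 0.9464/0.75 = 1.26. Losing all nine after T2, with T2–T3 correlation 0.5, gives 0.9286/0.7321 = 1.27. A higher T1–T3 correlation shrinks the loss: in completers the ratio is 2/1.7 = 1.18 at 0.7 and 2/1.8 = 1.11 at 0.8.

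**The case against.** The strongest reply is that the plan never states the free-baseline model. Putting T1 in the response does not by itself turn the arm effects into change-score contrasts. A model with T1 as a response and one T1 mean for both arms gives 0.75 in completers, the same as ANCOVA. This stands. The point is therefore conditional on the usual form being fitted, and what the documents themselves show is that the form is left open.

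A reader might also infer that the trial's power falls to 71%. The documents do not support that. Section 17.1 powers the week-4 ANCOVA, Section 17.4.2 plans that same ANCOVA, and no power is claimed for week 8.

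A reader might infer a general loss of precision for biomarkers. That is not supported either, since Section 17.4.3 already plans baseline-adjusted ANCOVA at 4 or 8 weeks. The T-cell assays in Section 4.4.3 are drawn only at baseline and week 4, so they have no week-8 contrast to lose. For other questionnaires, the methodology carried over from Aim 2 includes the ANCOVA.

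Finally, the estimate is unbiased under either form, the primary aim is feasibility, and Section 17.4.4 asks for cautious reading of secondary and exploratory results. All of this limits the consequence. It is not a reason to leave the form open when the more precise one uses the same data.

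**Conclusion.** The point holds as an improvement available at almost no cost; it is not an error in the primary analysis. Section 17.4.2 leaves baseline handling unstated in the only between-arm FACIT-F analysis that includes week 8.

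If the usual free-baseline form is fitted, the arm effects carry 1.33 times the necessary variance in 33 completers at a correlation of 0.50. At week 8 the figure is about 1.27 with the illustrative dropout. Over assumed T1–T3 correlations of 0.5 to 0.3, the week-8 excess is 33% to 54% in completers and 27% to 43% with dropout. If a common T1 mean was intended, there is no loss and the plan only needs to say so.

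The week-4 figure rests on the plan's own correlation. The week-8 figures rest on an assumed correlation, equal variances across visits and, where stated, an assumed dropout pattern. The estimate is not biased.

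**What to change.** In Section 17.4.2, state the mixed model's fixed effects and covariance structure, and choose one of two forms:

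- T1, T2 and T3 as responses, with one T1 mean common to both arms and arm effects at T2 and T3 only. This keeps the full T1–T3 trajectory, which is the stated purpose of the model, so it fits the plan better.
- T2 and T3 as responses, with T1-by-visit as a covariate. This is equally efficient in completers, but takes T1 out of the modelled trajectory.

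State that the week-4 and week-8 arm contrasts come from that model, with the week-4 ANCOVA remaining primary. Use the same form for the longitudinal models in Sections 17.4.3 and 17.4.4. For biomarkers the gain is confined to those longitudinal models.

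The cost is a sentence or two of wording. Data collection, sample size and software do not change.

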#### *17.4.3 Mechanistic aims*

We will assess the preliminary efficacy of the Mediterranean Diet intervention on metabolic measures including mitochondrial function from freshly isolated T cells. We will also obtain preliminary data on effects of the Mediterranean Diet vs. usual care on established metabolic biomarkers from blood samples. In an exploratory analysis, we will use similar models as in Aim 2 to assess Mediterranean Diet score with biomarkers of metabolic function. We will use both ANCOVA models looking at data at 4 or 8 weeks adjusting for baseline values, and longitudinal models incorporating data from time points T1-T3. This battery of biomarkers will be assessed to determine which are the most useful, and which others we should include in follow-up studies. Special statistical considerations may arise and will need be addressed during the analysis of biomarkers, including the need for transformation and missing data due to the detection limits.

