Aim 2: to evaluate the preliminary efficacy of a Mediterranean Diet vs. usual care to prevent cancer-related fatigue among patients with cancer undergoing chemotherapy, as assessed using the FACIT-F.

*We expect all measures of cancer-related fatigue to increase over the course of chemotherapy, though we hypothesize that the differences will be attenuated in the intervention group as assessed using the FACIT-F fatigue subscale score (primary aim: baseline to 4 weeks).*

Mechanistic Aim: to evaluate the effects of the Mediterranean Diet on mitochondrial function (i.e., mitochondrial stress test) and blood-based metabolic biomarkers (e.g., fasting blood glucose, insulin).

*The hypothesis is that, at 4 weeks, those in the Mediterranean Diet group will have T cells that exhibit higher ATP turnover, a higher spare respiratory capacity, and a smaller proton leak compared to the controls. We also hypothesize that those in the Mediterranean Diet group will have lower fasting blood glucose and lower fasting insulin concentrations than those in the control group at 4 and 8 weeks.*

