#### 4.2 Subject population

We will recruit 42 patients with cancer undergoing chemotherapy from Wilmot Cancer Institute or a satellite clinic (e.g., Pluta Cancer Center). In particular, these patients will have a recent diagnosis of cancer (any type except brain cancer), and will represent a broad range of patients seen at Wilmot Cancer Institute including young and old; men and women; those of various ethnic and racial categories (**Table 1**); those who are underweight, normal weight, and overweight; those with and without underlying metabolic dysfunction (e.g., diabetes); and those undergoing various types of chemotherapy treatment.

From previous local studies completed by our group, we expect a 20% withdrawal rate, resulting in approximately 33 participants with evaluable data (approximately 22 in the intervention group and 11 in the usual care group).

No vulnerable classes of subjects such as fetuses, neonates, children, pregnant women, prisoners, institutionalized individuals, or decisionally impaired adults will be recruited.

Total planned enrollment: 42 participants

**Table 1.** Targeted/planned enrollment by ethnic and racial categories:

Ethnic Category	Sex/Gender		
	Females	Males	Total
Hispanic or Latino	2	1	3
Not Hispanic or Latino	26	13	39
Ethnic Category: Total of All Subjects	28	14	42
Racial Categories			
American Indian/Alaska Native	0	0	0
Asian	2	1	3
Native Hawaiian or Other Pacific Islander	0	1	1
Black or African American	3	2	5
White	23	10	33
Racial Categories: Total of All Subjects	28	14	42

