**Why a randomized clinical trial and not a single arm feasibility study?** In order to evaluate the effects of the Mediterranean Diet on cancer-related fatigue, a control group is required to assess the change in fatigue over time without the intervention. If we determine that this study is not feasible and participants in the intervention group do not follow a Mediterranean Diet, we will still have important longitudinal data to correlate fatigue measures with diet metrics and metabolic measures over the course of chemotherapy.

**Why randomize 2:1?** Participants who sign up for a nutrition intervention study are often motivated to make dietary changes. By randomizing 2:1, each participant has a larger chance of getting the intervention and fewer participants will be disappointed not to receive the intervention right away. This ratio will still give us enough power (with n=42 participants total) to detect changes in fatigue. In addition, uneven allocation will provide us with more data about the intervention without increasing our sample size.

**Why provide food?** Meal planning, grocery shopping, and preparing food are large barriers dietary change, especially during chemotherapy. We believe that if we overcome these barriers to consuming the Mediterranean Diet at the onset of the intervention while we provide education, we will have greater adherence. In addition, meal provision is an established technique to facilitate behavior change, as people learn types of food that fit within the diet and serving size.

**Why include patients with underlying metabolic disorder? Will it reduce the ability to detect changes?** Diabetes is the most common metabolic disorder, and at least 15-20% of patients have diabetes as a co-morbidity with their cancer. The literature on the interaction between metabolic disease and supportive care outcomes is in its infancy, and while these conditions are complex, heterogeneous, and ever-changing, there are possible overarching interactions that could be curtailed with dietary interventions. We would like to recruit people with and without metabolic disease to ensure that this intervention is feasible among both, and in the future we would like to further investigate the specific interactions between cancer, preexisting metabolic disease, and cancer-related fatigue.

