#### *8.2.2 Source of record or measures*

The Clinical Record contains weight, height, current menopausal status, Karnofsky Performance Status (KPS) or Eastern Cooperative Oncology Group (ECOG) Performance Status, comorbidities, cancer stage, surgical procedures, types and doses of treatments, and other clinical characteristics. The study team will use the medical record to complete as much of this as possible. All other questionnaires will be completed by the participant, and all other measures will be obtained by the study team with the participant or the participants' blood samples.

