#### *8.2.5 Randomization procedures*

Randomization will be revealed to the participant at the end of the baseline assessments, before delivering the instructional portion of the intervention.

We will employ two treatment arms in a 2:1 allocation ratio:

1. Mediterranean Diet: an 8-week intervention entailing education of the Mediterranean Diet and delivery of Mediterranean Diet-inspired meals for 4 weeks.
2. Usual care: completion of assessments, with no intervention and usual care for their cancer.

Consented subjects will be randomized with a computer-generated random numbers table with block sizes of 3 and 6 and stratified based on how frequently they will be receiving chemotherapy (weekly, biweekly, or every 4 weeks vs. other). The random numbers tables will be generated centrally by [name], the project biostatistician, or a designee. A total enrollment of 42 subjects is planned.

Participants cannot be blinded due to the nature of the intervention. PI blinding is also not feasible given that the PI will play an active role in recruitment, intervention delivery, data acquisition, and analysis.

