### *17.2 Data Handling, Rigor, Quality, and Reproducibility:*

Data will be entered in REDCap electronic forms and electronically collated in a HIPAA-compliant REDCap database managed by our Division. After collation, data will be audited electronically and visually, as needed, for errors. Appropriate graphical or statistical diagnostics methods will be employed in each of the analyses to evaluate distribution of variables (e.g., to identify shape of the distribution and outliers) and also to evaluate the model assumptions (e.g., if deviation from the statistical assumptions is found, we will use alternative methods such as transformations or nonparametric analyses). Outliers that are detected will be investigated to determine if they are due to error. If not, analyses will be conducted with and without them to assess sensitivity. Because this is a preliminary efficacy study, unless stated otherwise, all hypothesis testing will be at the two-sided 0.15 level as appropriate for screening trials. SAS, JMP, and/or R software will be used for the analyses. Following the intent-to-treat principle, all randomized survivors will be analyzed in the arm as allocated, regardless of their compliance with the intervention or Mediterranean Diet contamination in the control group.

Although participants will be randomly assigned, differences may be present between study arms on demographic or clinical variables. Study arms will be compared on baseline demographic (e.g., age), clinical (e.g., cancer diagnosis, type of chemotherapy), and behavioral (e.g., physical activity, smoking) variables. If significant imbalance is found for a variable, it will be included as a covariate in subsequent analyses following standard practice.

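### The fasting glucose and fasting insulin comparisons have no rule for diabetes or injected insulin, although patients with diabetes are enrolled on purpose; a minor gap that is cheap to close

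*Combined protocol and SAP*

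**What the plan says.** Section 4.1 gives both markers a directional hypothesis: the diet arm "will have lower fasting blood glucose and lower fasting insulin concentrations than those in the control group at 4 and 8 weeks".

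Section 17.4.3 supplies the model: "We will use both ANCOVA models looking at data at 4 or 8 weeks adjusting for baseline values", together with longitudinal models over the three time points. That sentence follows one about relating diet score to biomarkers. I read it as covering the arm comparison too, because no other model is given for it.

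The sample is mixed by design. Section 4.2 includes "those with and without underlying metabolic dysfunction (e.g., diabetes" among the patients sought. Section 4.6 says that "at least 15-20% of patients have diabetes as a co-morbidity with their cancer". Its heading asks of this choice "Will it reduce the ability to detect changes", but the paragraph below answers on feasibility and future work and gives no analysis rule.

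Randomization is "stratified based on how frequently they will be receiving chemotherapy" (8.2.5), not by diabetes. Under 17.2, "all randomized survivors will be analyzed in the arm as allocated". The Clinical Record already holds "comorbidities, cancer stage, surgical procedures, types and doses of treatments" (8.2.2). Insulin therapy and other glucose-lowering drugs are not mentioned anywhere.

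**The concern.** Two separate problems follow.

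- **What is measured.** In a participant who injects insulin, serum insulin can reflect the product and the time of injection rather than the response to diet. Whether it does depends on the product and the assay, and the documents specify neither. A baseline value taken at a different interval from injection carries little information about the later one, so adjusting for it does not help.
- **Precision.** Glucose in treated diabetes sits higher and can be expected to vary more. Own-baseline adjustment captures part of that difference, and diabetes status would capture more.

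With 22 against 11 evaluable, single values carry weight. Section 17.4.3 uses the biomarker battery to decide which markers are worth carrying into later studies, so noise from one or two people could promote or drop a marker wrongly.

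**Working it through.** **The plan's own figure.** The only power statement is for FACIT-F: 22:11 evaluable, two-sided 0.15, effect 0.75 SD, correlation 0.50.
- SE = √(1 − 0.50²) × √(1/22 + 1/11) = 0.866 × 0.369 = 0.320.
- 0.75/0.320 = 2.35. Subtracting the critical value 1.44 leaves 0.91, so power is 0.817 (0.807 with the noncentral t on 30 df).
- The stated 80% is reproduced. No effect, SD or correlation is given for glucose or insulin, so everything below rests on assumptions.

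**Expected numbers.**
- With diabetes: 33 × 0.15 = 5.0 to 33 × 0.20 = 6.6. Among the 11 controls, 1.7 to 2.2.
- Insulin users, assuming 10-30% of those with diabetes: 33 × 0.15 × 0.10 = 0.5 to 33 × 0.20 × 0.30 = 2.0.
- Chance of at least one: 1 − (1 − 0.015)³³ = 39% to 1 − (1 − 0.06)³³ = 87%.

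**Leverage.** One control reading 5 SD high moves that arm's unadjusted mean by 5/11 = 0.45 SD.

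**Would the imbalance rule in 17.2 act?** Fisher's exact test at 22:11:
- Diabetes in 3/11 controls against 3/22 diet: p = 0.38.
- A single insulin user, in the control arm: p = 11/33 = 0.33.

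Neither reaches 0.15. One insulin user can never trigger the rule.

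**Insulin precision.** Simulated ANCOVA at 22:11, visit value on arm and baseline value. Assumptions: diabetes 15% or 20%; 20% or 30% of those on insulin; endogenous insulin lognormal, median 8 µU/mL, log-SD 0.6, within-person correlation 0.7; insulin users median 20 to 40 µU/mL, log-SD 0.8, correlation 0.

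| Scale | SE with insulin users ÷ SE without |
|---|---|
| Raw | about 1.4 to 2.7 |
| Log | about 1.05 to 1.09 |

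A repeat run gave 1.3 to 2.8 and 1.03 to 1.10, so the ends of these ranges are approximate.

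**Glucose precision.** Assumptions: mean 95, SD 10 without diabetes; mean 145, SD 30-45 with it; correlation 0.6. Adding a diabetes indicator to the baseline-adjusted model reduces the SE by about 8-11%. One setting: 5.11 to 4.71 mg/dL, and 1 − 4.71/5.11 = 8%.

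**Why a covariate alone is not enough for insulin users.** Stylized raw-scale case: true effect 0.75 SD (borrowed from FACIT-F), insulin users' readings 3 SD higher, varying between visits with 1 to 5 times the others' SD. Power without such patients is 0.79.

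| Insulin users | All kept | Indicator added | Users left out |
|---|---|---|---|
| 1 | 0.73-0.62 | 0.79-0.77 | 0.78-0.79 |
| 2 | 0.68-0.49 | 0.76-0.63 | 0.76-0.77 |
| 3 | 0.64-0.42 | 0.72-0.50 | 0.75-0.77 |

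The mean estimate stays between −0.69 and −0.73, against −0.74 with no insulin users. The average harm is lost precision, not systematic bias. In any one trial the error can go either way.

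**The case against.** The plan is not silent on difficult values. Section 17.2 has outliers that are not errors analysed with and without, and provides for transformation or nonparametric methods when assumptions fail. Section 17.4.3 names transformation for biomarkers. Section 4.4.4 promises to account for behavioral and clinical factors in estimating effects on metabolism, and 17.4.2, whose models 17.4.3 follows, adds patient covariates. These analyses are preliminary, 17.4.4 promises cautious interpretation of secondary and exploratory results, and no success criterion uses glucose or insulin.

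Much of this stands. A reader might infer that true extreme values simply stay in, that nothing beyond the baseline value can enter the model, or that a few insulin users will dominate the contrast. The documents do not support any of these. The first is contradicted by 17.2 and the second by 4.4.4 and 17.4.2. The third holds only on the raw scale under assumed inputs: on the log scale the excess is a few percent, and the sample may contain no insulin user.

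What remains is narrower. None of the provisions names diabetes or insulin. The outlier rule does not say which result prevails and misses a drug-driven reading that is not extreme. Transformation is optional. The imbalance rule will seldom fire at this size, and it addresses neither precision nor what the assay reads.

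**Conclusion.** The point holds as a minor improvement to a stated method. The fasting glucose and insulin contrasts pool participants with and without diabetes, the stated model adjusts for baseline value, and no rule is tied to diabetes or injected insulin although the data for one are largely collected already.

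The size depends on inputs the documents do not give: the insulin-treated share, the assay, the marker distributions and the correlations. The 15-20% is a general figure for patients with cancer, stated as a minimum, not a forecast for this trial. The log scale removes most of the precision loss for insulin. It does not change what is measured in someone injecting it.

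It would be wrong to infer that the trial's main results are at risk or that patients with diabetes should not be enrolled. Feasibility and FACIT-F do not use these markers, and the rationale for broad enrolment in 4.6 is unaffected.

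**What to change.** In 17.4.3:

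1. Include baseline diabetes status, from the Clinical Record, as a covariate in the glucose and insulin models.
2. Prespecify the log scale for fasting insulin, and for glucose if it is skewed.
3. Base the fasting-insulin contrast on participants not using injected insulin at baseline, and report the all-randomized analysis alongside. Do not exclude on insulin use that starts after randomization: the diet could itself influence it, and selecting on it would undo the randomized comparison. Handle it only as a sensitivity analysis.
4. Abstract glucose-lowering medication from the medical record at baseline and at each assessment.

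The cost is a few sentences, one abstracted item, one residual degree of freedom and perhaps one or two fewer participants in the insulin contrast, which would then not cover insulin-treated patients. Eligibility and clinical management do not change.
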